## 6. PROCEDURES

750 adults with a past history of stroke will be recruited to participate in the study. The study will take place at 4 sites, the University of Delaware (UD), the University of Pennsylvania (UPenn), Christiana Care Health System (CCHS) and Indiana University (IU). We anticipate 225 subjects will complete the study. The number recruited at each study site will be flexible as recruitment varies across sites. Subject numbers are monitored on an ongoing basis through the REDCap database. See information regarding recruitment methods in #7 below. All testing and training (intervention) sessions will occur at IU, UPenn and UD, while only training sessions will occur at CCHS with testing of CCHS subjects occurring at UD. Data collection sessions at the University of Pennsylvania were ended as of July 2020, but analysis of data collected at that site will continue through the end of the project.

We may recruit participants from the University of Delaware Stroke Research Registry (IRB# 1642798). Please see attached Study Approval Letter. Participants recruited through other means will be offered the opportunity to enroll in the Stroke Research Registry when they consent to this study. Lab members will be instructed to emphasize that enrolling in the Registry is completely voluntary and the participant's choice to enroll or not has no effect on their participation in this study or any other studies conducted at the University of Delaware.

Regardless of recruitment method, during the initial phone call or email a member of the research team will describe the purpose and general procedures of the study. We will explain what to expect and the potential risks and benefits of participation. We will also inform the potential participant that joining the study is completely voluntary and that he/she is free to reconsider or stop participation at any time. If the potential participant expresses interest in agreeing to join, we will then proceed with a series of screening questions to determine if the person might be eligible (see Appendices). For subjects that do not appear to be eligible, screening forms will be destroyed. No additional documentation (e.g.- consent forms, HIPPA forms) will be handled by UD in regards to UPenn or IU subjects.

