## **Testing Procedures**

***Baseline evaluation session.*** Subjects will undergo a brief battery of clinical assessments conducted by a trained member of the research team. Clinical assessments will include collection of medication and co-morbidity information, blood pressure, heart rate and body mass index, the 10 meter walk test, the 6 minute walk test, the Activities Specific Balance Confidence scale (ABC), the Patient Health Questionnaire nine-item depression scale (PHQ-9), and the Montreal Cognitive Assessment (MoCA) (see Appendices). In addition, subjects will be provided with a Stepwatch Activity Monitor and/or Fitbit activity monitor and instructed in its wear and use. Subjects will wear the monitor for 1 week. Following this baseline evaluation session and the 1 week step monitoring, the inclusion criteria of walking speed between 0.3 and 1.0 m/s and steps/day less than 8000, can be evaluated and continued eligibility confirmed. If subjects do not meet these criteria after evaluation, they will be withdrawn from the study.

If any subject scores  $\geq 5$  on the PHQ-9, they will be informed of their score and advised to discuss this with their primary physician. In addition, for any participant endorsing suicidal ideation on one or more test items on PHQ-9, (1) we will notify the physician and (2) we will give the participant the telephone number for Crisis Intervention Services of Northern Delaware ([[contact]]([contact]) or [[contact]]([contact])) which is staffed 24 hours/day, 7 days a week, to whom they can reach out if they feel desperate, hopeless and/or at risk for suicide. This is standard procedure for clients in the Physical Therapy Clinic.

Symptom limited graded exercise test. Prior to beginning the intervention, all subjects will undergo a symptom limited graded exercise test (GXT) on a motorized treadmill in the Nurse Managed Health Center (NMHC) under the supervision of a nurse practitioner and an exercise physiologist. During the GXT a 12 lead electrocardiogram and breath by breath analysis of oxygen consumption with a metabolic cart will be recorded. The results of the test will be reviewed by a cardiologist for abnormal responses that would prevent the subject from safe participation.

Subjects will have up to 5 ml of blood drawn by a trained practitioner in the NHMC for measurement of blood lipids and glucose at each of the testing time points (baseline, post-intervention and 6 and 12 month follow-up evaluation sessions).

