Post-intervention and follow-up evaluations. Post, 6 and 12 month evaluation sessions will be identical to the baseline evaluation including the graded exercise test for the purposes of measuring changes in oxygen consumption that may have occurred with the intervention and measurement of blood lipids and glucose.

In order to examine the potential secondary prevention benefits of the intervention, at the 6 and 12 month follow-up appointment subjects will be asked about major adverse cardiovascular and cerebrovascular events (MACCE); specifically if they have had: recurrent stroke, myocardial infarction, unstable angina requiring hospitalization or peripheral artery event and the date of that event. This data will be confirmed for accuracy through contact with the subject's physician. Phone follow-up at 2 years will be completed for subjects enrolled in the first 2 years of the study to collect longer term follow-up data on these events. Information received from subjects will be confirmed by their physician (see Appendices). If subjects have any of these events during the course of the study, they will be withdrawn from all testing and training, except we will continue to track them for MACCE.

Decisions will be made regarding withdrawing subjects at 6 and 12 months by gathering medical record information as needed for subjects who report changes in their health history. Self-reported and non-physical measures may still be collected at 6 and 12 month time points even if they are not able to perform physical testing.

In addition to the 6 and 12 month follow-up, subjects will be contacted by the Stroke Studies Coordinator at UD at 4.5, and 9 months post baseline testing to check in as a means to improve subject retention. Subjects will be told that we are calling to check in. We will ask them if anything has changed since their last visit/phone call, including address, contact information, physician. Any changes in this information will be updated in the database.

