#### 14. Other IRB Approval

**Has this protocol been submitted to any other IRBs?** This study has been approved by the University of Pennsylvania's and Indiana University's IRB and that approval has been submitted as an amendment to this protocol. An Institutional Review Board Authorization Agreement has been signed between CCHS and UD.

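### The only crisis line named for participants who endorse suicidal ideation is a Northern Delaware service, although Indiana University, and UPenn until July 2020, also test participants

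*Combined protocol and SAP*

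**What the plan says.** The rule is in the current protocol, section 6, Testing Procedures, under the baseline evaluation session. It applies "for any participant endorsing suicidal ideation on one or more test items on PHQ-9", with no restriction by site, and has two parts: "1) we will notify the physician and (2) we will give the participant the telephone number". The service is then named: "we will give the participant the telephone number for Crisis Intervention Services of Northern Delaware". The protocol adds that the line is staffed at all hours and that the step is routine in the Physical Therapy Clinic. Separately, anyone scoring 5 or more on the PHQ-9 is told the score and advised to raise it with their primary physician.

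On sites, section 6 states: "All testing and training (intervention) sessions will occur at IU, UPenn and UD". Christiana Care (CCHS) provides training only, and its participants are tested at UD. For UPenn, "Data collection sessions at the University of Pennsylvania were ended as of July 2020".

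On timing, the paragraph on follow-up evaluations says: "Post, 6 and 12 month evaluation sessions will be identical to the baseline evaluation".

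On oversight, section 14 records: "This study has been approved by the University of Pennsylvania's and Indiana University's IRB".

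**The concern.** A rule written for every participant at every testing site names one crisis service, and that service belongs to the lead site's region. The protocol treats the crisis number as a separate action from telling the physician. It is what the participant holds if they feel at risk at night or over a weekend, when a notified physician may not be reachable. If the line is less able to help a caller from another state, the second safeguard is weaker at IU, and was weaker at UPenn, than at UD. What is at stake is participant safety. No outcome, estimate or test is affected.

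**Working it through.** No sample size, power or alpha figure is involved, so the check sets the relevant sections side by side and counts sites and visits.

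**1. Could a second contact be hidden by redaction?** Two contact entries are masked. Both sit in the parenthesis directly after the Northern Delaware service, so both belong to it. No other crisis service appears anywhere in the supplied text.

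**2. Which testing sites lie outside Delaware?** Inputs are section 6 of the 2016 and current protocols and the Summary of protocol changes. State is taken from the institutions' names.

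| Period | Testing sites | Outside Delaware |
|---|---|---|
| 2016 protocol | UD, UPenn | 1 of 2 (UPenn) |
| IU added (approved 10/16/2018) to July 2020 | UD, UPenn, IU | 2 of 3 (UPenn, IU) |
| After July 2020 | UD, IU | 1 of 2 (IU) |

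At least one testing site has therefore been outside Delaware in every period.

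**3. How often can the step arise?** The PHQ-9 is in the baseline battery and the later evaluations repeat that battery: baseline + post + 6 months + 12 months = 4 occasions per participant at most. Self-reported measures may also be collected at 6 and 12 months from people who cannot do the physical tests.

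**4. Was the sentence adapted as sites changed?** The 2016 protocol has the same crisis sentence, and UPenn was already a testing site. The current baseline section differs from the 2016 one in other respects: the activity monitor, the walking-speed range and the stated blood volume. The crisis sentence is unchanged, although IU was added in between.

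**5. Does the protocol mark arrangements that apply only at UD?** It does so elsewhere. Section 10 (Data) describes storage of identity files for UD and CCHS participants and says that UPenn and IU have similar processes. Section 11 (Confidentiality) does the same for the code key. The crisis rule carries no such qualifier.

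**6. How many participants are affected?** This would need the number tested at IU and UPenn and the proportion endorsing the item. Section 6 leaves recruitment per site flexible, and the documents give no endorsement rate, so no count is offered.

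**The case against.** The strongest reply is that this is UD's own IRB form and that the baseline section describes the lead site's facilities. It refers to one Physical Therapy Clinic, and the graded exercise test is placed for all subjects in one Nurse Managed Health Center, which cannot be literally true if IU and UPenn run their own testing. On that reading, other sites use equivalents. IU and UPenn have their own IRB approvals, section 6 says UD handles no consent or privacy forms for their participants, and local crisis contacts would plausibly sit in those local submissions. The Delaware line suits UD and CCHS participants, all of whom are tested at UD. In addition, physician notification is required everywhere, nothing forbids staff from giving another number, and the SAP's references to a final 2023 protocol and to the end of the study suggest that an amendment may come too late.

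Much of this stands. It limits the finding to what this protocol instructs; it does not show what IU and UPenn staff did. It does not remove the gap, because the rule covers any participant and the same document says so when an arrangement is confined to UD. Physician notification is a real safeguard, but the protocol itself requires a direct contact as well. The advice for scores of 5 or more depends on the total score, so it need not reach everyone who endorses ideation.

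**Conclusion.** The concern holds as a minor safety point. As written, the rule gives participants at one of the two remaining testing sites (two of three while UPenn was active) a crisis line named for another region, and that line is the only 24-hour contact handed to them. The step can arise at up to four evaluations per participant.

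The conclusion is bounded in three ways:

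- Local IRB submissions and appendices were not available and may already name local services.
- The documents do not say whether the Delaware line serves callers from elsewhere; that it would be less useful to them is an assumption.
- Nothing shows that any participant went without suitable help.

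The statistical analysis is untouched.

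**What to change.** If testing is still open, amend the baseline evaluation paragraph so that the contact given is the one that applies at the participant's testing site. This can be a local line per site, in the text or a short site appendix, or one national 24-hour line. Keep the physician notification unchanged, and leave the choice of service to the clinical team and the local IRBs. The cost is one line or a short appendix plus an IRB amendment; no assessment or analysis changes.

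If testing has finished, no amendment is needed. The sponsor should ask IU and UPenn which contact their staff gave and file the answer with the study record.

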(FAST+SAM) is superior in improving real-world walking activity compared to fast walking training alone (FAST) or a step activity monitoring and feedback program alone (SAM) in those with chronic stroke. Using a randomized controlled experimental design, 225 chronic (> 6 months) stroke survivors, will complete approximately 12 weeks (goal of 36 sessions) of fast walking training (FAST), a step activity monitoring program (SAM) or a fast walking training + step activity monitoring program (FAST+SAM). The primary (steps per day), secondary (self-selected and fastest walking speed, walking endurance, oxygen consumption) and exploratory (vascular events, blood lipids, glucose, blood pressure) outcomes will be assessed by blinded evaluators prior to initiating treatment, after the last treatment and at a 6 and 12 month follow-up. Moderation of specific intervention outcomes by baseline characteristics will be evaluated to determine *for whom* the interventions are effective. Following completion of this study, we will not only understand the efficacy of the interventions and the individuals for which they are effective, we will have the necessary information to design a study investigating the secondary prevention benefits of improved physical activity post-stroke. This study is, therefore, an important step in the development of secondary prevention guidelines for persons with stroke.

[figure not shown]

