**How will data be analyzed and reported?**

Appropriate statistical analysis of the primary (General Linear Mixed Modeling) and exploratory (Cox Proportional Hazards Model and a Generalized Estimating Equation) outcomes will be completed under the direction of the biostatistician on the project. The results will be reported to professionals interested in research via journals and presentations.

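### MACCE has no death component and is found by asking participants, so fatal vascular events can be missed, and no rule for death in the Cox model is given

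*Combined protocol and SAP*

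**What the plan says.** Section 6 of the final protocol (Testing Procedures, post-intervention and follow-up evaluations) has participants questioned about MACCE at the 6- and 12-month visits: "specifically if they have had: recurrent stroke, myocardial infarction, unstable angina requiring hospitalization or peripheral artery event and the date of that event". The 2016 protocol has the same list. Three further provisions apply:

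- Longer follow-up: "Phone follow-up at 2 years will be completed for subjects enrolled in the first 2 years of the study".
- Verification: "Information received from subjects will be confirmed by their physician".
- After a MACCE, participants stay under observation: "they will be withdrawn from all testing and training, except we will continue to track them for MACCE".

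Section 7 gives study staff access to records and hospital-admission alerts through the Delaware Health Information Network (DHIN). This covers UD and CCHS participants who agree and who enrolled after that amendment.

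On analysis, section 10 offers only the phrase "exploratory (Cox Proportional Hazards Model and a Generalized Estimating Equation) outcomes". The SAP excerpt covers Aims 1 and 2 and contains no MACCE analysis. The abstract (item 5) classes vascular events as exploratory and says that on completion "we will have the necessary information to design a study investigating the secondary prevention benefits" of greater activity after stroke.

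**The concern.** Someone who dies cannot answer a question at a visit. If the first vascular event is fatal, the procedure as written has no step that would bring it into the data. A vascular death that fits none of the four listed terms, such as a sudden cardiac death without a diagnosed infarction, would not count even if it became known.

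What is at stake is mainly the event rate. These data are collected to look at secondary prevention, and the abstract presents the trial as groundwork for a study of that question. A rate that lacks fatal events is too low for that purpose. Separately, a Cox model needs a stated treatment of death, and none is visible.

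**Working it through.** **Step 1. Could any described source find a fatal first event?**

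| Source | What starts it | Would it reveal a fatal first event? |
|---|---|---|
| Questions at 6 and 12 months | Participant attends and answers | No |
| 2-year call | Participant answers; early enrollees only | Not by design; no proxy interview is described |
| Physician contact for MACCE | A participant's report to be confirmed | Not as written |
| Record gathering at 6 and 12 months | Participant reports a change in health | Not as written |
| Calls at 4.5 and 9 months | Retention check-in | Possibly by chance; no vital-status question is listed |
| Tracking after a MACCE | A MACCE already known | Does not apply to a first event |
| DHIN records and alerts | Agreement; UD or CCHS; enrolled after the amendment | Sometimes; not named as a MACCE source, does not cover UPenn or IU, and alerts concern admissions |

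No vital-status check, proxy report or cause-of-death procedure appears. Fatal events can be missed, and the chance of finding one differs by site.

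**Step 2. Size.** The documents give no MACCE rate, fatal share, hazard ratio or power, so there is no figure to reproduce. What follows is illustration.

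Inputs: N = 225 (planned completers, section 6 and SAP power section). Assumed: 12-month vascular risk r = 3% to 10%, fatal share f = 10% to 30%, every fatal event missed.

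- All events, N × r: 225 × 0.03 = 6.75; 225 × 0.10 = 22.5.
- Events lost, N × r × f: 6.75 × 0.10 = 0.675; 22.5 × 0.30 = 6.75.

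So about 0.7 to 6.8 of 6.8 to 22.5 events are lost, and the observed rate is low by the factor 1 − f (0.90 to 0.70). Someone who dies during follow-up is not a completer, so the number randomised is the proper base; the counts scale in proportion to it.

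**Step 3. Effect on a later study.** If that study counts fatal events but is sized from a rate without them, the number of participants for a fixed number of events is overstated by 1/(1 − f): 1/0.90 = 1.11 to 1/0.70 = 1.43.

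**Step 4. Effect on the arm comparison here.** Assume HR 0.5, two-sided 0.05 (no exploratory alpha is given) and two-thirds of the events in any one pair of arms. Schoenfeld power is Φ(√(d/4) × |ln HR| − 1.96).

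- r = 3%: d = 6.75 × 2/3 = 4.5, power 0.11; with fatal events lost, 0.09 to 0.10.
- r = 10%: d = 22.5 × 2/3 = 15, power 0.27; with fatal events lost, 0.20 to 0.25.

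Eighty per cent power needs 66 events in the pair. The comparison is uninformative with or without the fatal events, so the rate is where the omission matters.

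**The case against.** The strongest reply has four parts.

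*A fatal stroke or infarction already meets the definition.* This stands: the listed terms are not limited to non-fatal events. A reader might infer that fatal strokes and infarctions are always missed. The documents do not support that, because DHIN records or a physician could reveal some. They can be missed; the weakness for these two is in finding them. Other vascular deaths have no place in the definition.

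*No censoring rule is stated.* Also correct. A reader might infer that deaths enter the Cox model as ordinary censoring. That is a common default, but the text gives no rule. Nor is such censoring wrong in itself: a cause-specific hazard for MACCE is estimated by censoring non-vascular deaths. An undetected fatal MACCE is primarily an error of outcome ascertainment. A distorted hazard ratio cannot be claimed either. With f = 20% in the reference arm and an HR of 0.7 for non-fatal events, the overall HR is about 0.8 × 0.7 + 0.2 × 1.0 = 0.76 if treatment leaves fatal events unchanged, and stays at 0.7 if it affects both alike. Nothing in the documents points to a difference.

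*The missing detail may be elsewhere.* The SAP is an excerpt, and the appendices and monitoring-board charter are not shown. This limits the point about the Cox model to the visible text. It does not alter the event list or the described route of collection.

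*The endpoint is exploratory, and the abstract does not say that the MACCE rate will size the next trial.* True, and it keeps the point small.

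Larger losses can be produced by choice of assumptions. Non-fatal MACCE of 3–8% and deaths of 2–5%, half of them vascular, give 2.25/(2.25 + 18) = 11% up to 5.6/(5.6 + 6.75) = 45% of vascular events missed. Those ends pair a low rate with a high one. Pairing low with low and high with high gives 2.25/(2.25 + 6.75) = 25% and 5.6/(5.6 + 18) = 24%.

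**Conclusion.** The point holds as a minor one. MACCE lists no death component, the only described way of finding events is the participant's own report, and physician contact is confined to confirming it. DHIN access is partial by site, consent and enrolment date, and is not tied to the endpoint. Fatal vascular events can be missed, which biases the exploratory event rate downward, and how death enters the Cox model is unspecified in the visible text.

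The size rests wholly on assumptions. With a 12-month vascular risk of 3–10%, 10–30% of events fatal and all of those missed, the loss is about 0.7–6.8 of 6.8–22.5 events among 225. Any fatal event found through DHIN or a physician reduces it. The primary steps-per-day analysis and its sample size do not depend on this endpoint.

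**What to change.** 1. Count vascular death, including fatal stroke and fatal myocardial infarction, as MACCE.
2. Establish vital status, and the date and cause of any death, for every randomised participant at all sites. Use the physician contact already in place, a proxy, or records where available. DHIN cannot be the sole route because UPenn and IU are outside it.
3. State in the SAP that non-vascular deaths are a competing event, and report cumulative incidence alongside the cause-specific hazard.
4. Report time to MACCE or any death as a sensitivity analysis. It does not depend on the classification of cause of death.

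The cost is protocol and SAP wording plus a physician or proxy contact for the few participants who cannot be reached. Deaths can still be traced retrospectively, provided the rule is fixed before the MACCE analysis is run.
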